2. EXPLORATORY SCIENTIFIC HYPOTHESES, OBJECTIVES, AND ENDPOINTS

Measurement of B & T-cell subsets and flu-specific responses as a way of understanding immunosuppression in this patient population, correlating with influenza-like illness.

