6.5 Schedule of events

Experimental arm

Assessment	Screening + First visit	Week 5 ^a	Week 9 ^a	Week 17 ^a	Week 21 ^a
Signed informed consent	X				
Vital signs	X				
CBC/d/p ^d	X				
CRP, Serum IG's, LDH	X				
Myeloma proteins ^e	X				X
Blood for research ^f	40 mL	40 mL			40 mL
Fluzone HD	X		X	X	
Prevnar (PCV13)		X			
Record grade \geq 2 adverse events ^g	X		X	X	
Influenza-like illness update ^b		X	X	X	X
PFS and OS ^h					X

Control arm

Assessment	Screening + First Visit	Week 5 ^a	Week 9 ^a	Week 17 ^a	Week 21 ^a
Signed informed consent	X				
Vital signs	X				
CBC/d/p ^d	X				
CRP, Serum IG's, LDH	X				
Myeloma proteins ^e	X				X
Blood for research ^f	40 mL	40 mL			40 mL
Fluzone HD	X				
Prevnar (PCV13)		X			
Record grade \geq 2 adverse events ^g	X				
Influenza-like illness update ^b		X	X	X	X
PFS and OS ^h					X

- a. Assessments on these days can be performed within a \pm 5 day window. Subsequent visits (weeks 5, 9, 17, 21) are based on the actual time of Fluzone HD vaccination, not the pneumonia vaccination.
- b. Involves contact between study personnel and the patient regarding influenza-like illness and SAEs. An in-person visit is not required.
- c. All patients (N=148) will have research blood drawn for correlative science. In both arms, blood will be obtained at baseline, week 5, and week 21. The first 20 patients in each group (n=40 total), split evenly between intervention arm (20 experimental, 20 control), had additional blood drawn 1 week after each Fluzone HD dose (week 2 for control arm and weeks 2, 10, and 18 in the experimental arm) – this was completed 17-Nov-2019.
- d. CBC, differential, and platelets will be performed pre-vaccination.
- e. If not done with results available within 30 days of initial vaccination, a modified myeloma disease assessment requested but not required to include SPEP and free light chains if either were measurable per IMWG criteria in the past. Serum IgD or IgE are requested if a monoclonal IgD or IgE were present in the past. For patients with an IgA monoclonal protein, Hevylite IgA can be used to replace serum immunoglobulins and SPEP.
- f. Peripheral blood samples will be obtained and analyzed as described in correlative science section.

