7.1.5 Expected adverse events / toxicities

Adult recipients of inactivated influenza virus vaccines may develop influenza-like reactions such as fever, feverishness (chills/shivering/sweating), gastrointestinal side effects (emesis and diarrhea), fatigue (tiredness), malaise (general unwell feeling), myalgia (body aches/muscular pain), arthralgia (joint pain), headache, and/or nausea. Some subjects may develop reactions at the injection site, including pruritus (itching), ecchymosis (bruising), erythema (redness), induration (hardness)/swelling, pain, and/or tenderness. With unadjuvanted licensed, inactivated influenza virus vaccines most of these reactions peak in intensity in the first 24 hours after vaccination and usually disappear without treatment within 1 or 2 days. Analgesics (e.g., acetaminophen, or ibuprofen or similar non-steroidal anti-inflammatory drugs (NSAIDs)) and rest may generally relieve or lessen these reactions. Bruising can sometimes occur due to the vaccination procedure.

In addition, post-marketing surveillance indicates the following adverse events of special interest (AESI) as potential risks for pandemic vaccines based on those identified for the seasonal influenza vaccines: neuritis, convulsions, severe allergic reactions, encephalitis, thrombocytopenia, vasculitis, and Guillain-Barré (GBS) syndrome. Reports of these reactions were rare; however, exact incidence rates cannot be precisely calculated.

Acute and potentially life-threatening allergic reactions are also possible. Very rarely, occurring in about 1 in 4 million people given a vaccination, there can be a serious allergic reaction to a vaccine. These reactions can manifest as skin rash (hives), swelling around the mouth, throat or eyes, difficulty breathing, a fast pulse, or loss of blood pressure. If these reactions occur, they can usually be stopped by the administration of emergency medications by the study personnel. As with any vaccine or medication, there is a very small chance of a fatal reaction (death), although researchers do not expect this to occur.

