10.4.5 Analysis of influenza response and disease status endpoints

HAI will first be measured and summarized with mean and standard deviation at different time-points, respectively. Paired t-test will be further used to test whether there is significant change in HAI at different time points from baseline, respectively. Two sample t-test will be used to compare the change in HAI from baseline between two groups, at different time-point, respectively. Chi-Square test will be used to compare the Seroconversion and Seroprotection between two groups, respectively. Logistic regression model will be used to compare adjusted difference in Seroconversion and Seroprotection between two groups after adjusting for other factors, respectively.

Spearman/Pearson correlation coefficient will be used to measure the relationship between correlation between HAI, predefined risk of influenza-like illness (low, moderate, high), respectively. Finally Mixed model will be employed to test their correlations over the whole period with and without

adjusting for other factors, respectively. Kaplan Meir method, Log-rank test, and Cox model will be used to test the relationship between peak HAI and PFS.

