10.5.2 Evaluation of success of blinding (N/A)

10.5.3 Breaking the study blind / participant code (N/A)

11. ADVERSE EVENTS: LIST AND REPORTING REQUIREMENTS

11.1 Identification of AEs and follow-up

The occurrence of an AE or SAE may come to the attention of study personnel during study visits and interviews of a study participant presenting for medical care, or upon review by a study monitor.

The only adverse events to be captured in this protocol must relate to vaccination or influenza-like illness, and these will be captured on the appropriate CRF. Changes in the severity of these AE's only will be documented to allow an assessment of the duration of the event at each level of severity to be performed. These AEs will be followed to adequate resolution.

Information to be collected includes event description, time of onset, clinician assessment of severity, relationship to study product (assessed only by those with the training and authority to make a diagnosis), and time of resolution/stabilization of the event.

Any medical condition that is present at the time that the participant is screened will be considered as baseline and not reported as an AE. Unanticipated problems will be recorded in the data collection system throughout the study.

The site PI will record all reportable events with start dates occurring any time after patient receives the any study drug until 7 (for non-serious AEs) or 14 days (for SAEs) after the last day of study participation. At each study visit, the investigator will inquire about the occurrence of AE/SAEs since the last visit. Events will be followed for outcome information until resolution or stabilization.

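### The exploratory aim is to relate immune response to influenza-like illness, but 10.4.5 uses an undefined risk class in place of the illness observed, and leaves out the B- and T-cell measures

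*Combined protocol and SAP*

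**What the plan says.** Section 2 consists of a single aim: "Measurement of B & T-cell subsets and flu-specific responses as a way of understanding immunosuppression in this patient population, correlating with influenza-like illness".

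The schedule of events (6.5) has an ILI update at weeks 5, 9, 17 and 21 in both arms. Its footnote b describes the update: "Involves contact between study personnel and the patient regarding influenza-like illness and SAEs". ILI is also within the scope of adverse-event capture under 11.1: "The only adverse events to be captured in this protocol must relate to vaccination or influenza-like illness".

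The analysis is in 10.4.5. It begins "Spearman/Pearson correlation coefficient will be used to measure the relationship between correlation between HAI", and the second variable is "predefined risk of influenza-like illness (low, moderate, high". It then moves to a mixed model: "Finally Mixed model will be employed to test their correlations over the whole period with and without" adjustment for other factors. The only other model that uses biomarkers is the Cox model in 10.4.6, whose outcomes are TTP, PFS and OS.

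**The concern.** There are three gaps between the aim and the analysis.

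- **The variable is undefined.** It is called predefined, yet the documents give no criteria, inputs, cut-offs or time of assignment for its three levels. It cannot be programmed as it stands, and it could be built after titres are known.
- **It is not the outcome.** Even a well-defined risk class says who was expected to fall ill, not who did. Section 2 asks about the illness itself.
- **The predictors are incomplete.** Section 2 names B- and T-cell subsets, and 10.4.5 uses HAI only.

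At stake is whether the trial can say anything about immune response and illness from data it already collects. Dropping raw ILI reports into the whole-period mixed model would not be a clean repair, because week-21 titres would then be related to illnesses that came before them.

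**Working it through.** The plan states no figure for this analysis, so the main check sets the sections side by side. The arithmetic only gives the scale.

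**1. Is the risk class defined anywhere?** The eligibility criteria (4), schedule (6.5), correlative studies (8), response definitions (9) and statistical section (10) were read for it. It appears only in 10.4.5.

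**2. Is observed ILI analysed against immune response anywhere?**
- 10.4.5: HAI against the risk class, then a mixed model of the same pair. No ILI event variable.
- 10.4.6: biomarkers against TTP, PFS and OS. No ILI.
- 10.4.2: adverse events described by cohort. ILI may appear here through 11.1, but with no link to HAI or cell measures.

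No section makes the link, and none gives a case definition for ILI.

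**3. Time order.** Research blood is drawn at baseline, week 5 and week 21. The ILI updates end at week 21, so the week-21 sample follows essentially all recorded illness and cannot predict it. The week-5 sample precedes the remaining follow-up, and by then both arms have had one Fluzone HD dose.

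**4. Expected patients with ILI.** Inputs: 134 observations (10.3) and a 20% ILI likelihood (3.5). The 134 itself reproduces: 120.4 before adjustment, divided by (1 − 0.1), is 133.8. The 20% is for myeloma patients on treatment, with no follow-up period stated. Applying it trial-wide is an assumption, because any plasma cell dyscrasia is eligible.
- Whole period: 0.20 × 134 = 26.8. At 10%, 13.4; at 30%, 40.2.
- After week 5, at a constant rate: 16 of the 20 weeks remain, so 26.8 × 16/20 = 21.4.

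**5. Precision of a descriptive arm difference over the whole period**, with 67 per arm and the same rate in each:
- At 20%: 1.96 × √(2 × 0.2 × 0.8 / 67) = 0.135, or ±13.5 points.
- At 10%: 1.96 × √(2 × 0.1 × 0.9 / 67) = 0.102. At 30%: 1.96 × √(2 × 0.3 × 0.7 / 67) = 0.155.

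This half-width applies to a simple difference in proportions. It does not describe the post-week-5 association with immune measures.

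**6. How many of these illnesses would be influenza?** Section 3.5 puts influenza at 3–5% of such viral illnesses: 26.8 × 0.03 = 0.8 and 26.8 × 0.05 = 1.3, so about one patient.

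**7. Time near a dose.** The experimental arm has two further Fluzone HD doses after week 5, at weeks 9 and 17; the control arm has none. With a 7-day window per dose, the excluded time after week 5 is 2 × 7 = 14 of 16 × 7 = 112 days (12.5%) against 0 of 112.

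**The case against.** The strongest reply is that this is one exploratory sentence outside the primary endpoint, that the sentence in 10.4.5 is garbled, and that observed ILI may have been meant. A risk class might also be derivable from baseline data such as blood counts and immunoglobulins, so defining it would be a simpler repair. The exploratory status stands and limits the weight of the point. The rest does not close the gap: the text does not say that observed ILI is meant, and a defined class would still not be illness.

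A reader might infer four stronger things that the documents do not support.

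- **That the ILI data go wholly unused.** ILI falls under adverse-event capture in 11.1 and may be described by cohort under 10.4.2. Time of onset is already required for captured events. What is missing is the link to immune response.
- **That infection raising HAI would seriously distort the result.** By the protocol's own 3–5%, this concerns about one patient. The time-order argument against week-21 predictors does not depend on it.
- **That vaccine reactions will be counted as ILI.** Section 7.1.5 does warn of a resemblance: "Adult recipients of inactivated influenza virus vaccines may develop influenza-like reactions such as fever". The experimental arm also has more doses. But 6.5 has a separate adverse-event row, with a check 7 days after each Fluzone HD dose, and 11.3 requires a clinician's judgement of cause. Reactions last 1–2 days (3.8.1), so relabelling every illness within 7 days would be too blunt for the main analysis.
- **That the trial's main conclusion is at risk.** The week-21 seroprotection comparison and its sample size do not use ILI.

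One further criticism applies to the remedy itself: replacing the risk class with ILI that has no case definition would exchange one undefined variable for another. That stands, and the fix below includes a definition.

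**Conclusion.** The concern holds in this form: followed exactly, 10.4.5 does not answer the aim in section 2. It analyses HAI only, against a class that is defined nowhere, and no other section relates observed ILI to HAI or to the B- and T-cell measures. It should be corrected, but it does not touch the primary comparison.

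The size is modest. On the assumed trial-wide 20% rate, about 27 of 134 patients would have ILI over the whole period (13 to 40 at 10% to 30%) and about 21 after week 5 at a constant rate. That is enough for an exploratory estimate, not for a firm conclusion. ILI is also a non-specific outcome, since few such illnesses are influenza, so a weak association with HAI would be hard to interpret.

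**What to change.** In 10.4.5:

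1. Replace the risk class with observed ILI from the scheduled updates, with a stated case definition and an onset date.
2. Relate week-5 log2 HAI and week-5 B- and T-cell measures to first ILI after week 5 and up to week 21, adjusted for arm. With about 21 events, enter one immune measure at a time. Do not use week-21 titres as predictors of earlier illness.
3. Report ILI by arm descriptively, as a difference with a 95% CI.
4. As a sensitivity analysis only, exclude ILI that starts within 7 days of a Fluzone HD dose, together with that person-time.

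The cost is a rewording of 10.4.5, a case definition, and an onset date on the ILI update. Onset is already asked for where ILI is captured as an adverse event. No visit, sample or change in sample size is needed.

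The plan should state the downsides: few events, a non-specific outcome, week-5 measures that cannot show the effect of the later doses, and a sensitivity analysis that removes 14 of 112 days in the experimental arm and none in control, with any true ILI in those days.

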1. PRIMARY HYPOTHESES, OBJECTIVES, AND ENDPOINTS

Clinical		
Hypothesis	Objective	Endpoint
Continuous FluZone HD throughout the flu season will improve hemagglutination inhibition (HAI > 40) as measured at the end of the season compared to those patients that receive FluZone HD once.	Demonstrate an absolute 25% increase in seroprotection, defined as HAI>40 against all strains, at week 21 in the experimental arm compared to the control arm.	HAI will be measured in all patients at baseline, week 5, and week 21 to calculate seroconversion at week 5 and seroprotection at week 21. Seroconversion: Pre-vaccination HAI<10 and a post-vaccination HAI>40 or a pre-vaccination HAI >10 and a \geq 4-fold rise in post-vaccination HAI at week 5.

The above measurables will appear in the results section of www.clinicaltrials.gov at trial completion

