4.2.4 Expected survival < 9 months

4.2.5 Prisoners

5. REGISTRATION, ACCRUAL, AND EARLY TERMINATION

5.1 Accrual

5.1.1 Enrollment overall

The research team member obtaining informed consent will tell the patient that (1) participation is voluntary, (2) participation or non-participation will not affect their usual care and management, and (3) patient confidentiality will be maintained if the results of the study are published. The potential toxicities of protocol therapy and the study calendar will be explained to the potential participant. Patients will be provided with a consent form to review, and an opportunity to discuss the study and have all questions answered.

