5.3 Duration of follow-up

Patients will be followed for 4 weeks after removal from study and patient records will be reviewed until death or 2 years from enrollment (whichever comes first) to assess progression and survival. Patients removed from study for unacceptable adverse event(s) will be followed until resolution or stabilization of the adverse event.

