6.1.2 Control arm – Single Fluzone HD

Fluzone HD vaccine once at the time of enrollment for a total of 1 dose.

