9. RESPONSE

Time to progression (TTP): Time to progression is defined as the time from last treatment until progression. Patients who have died without evidence of progression are censored in the TTP analysis at the time of death and patients who are alive without progression are censored at the last disease assessment.

Progression-Free Survival (PFS): Defined as the time from last treatment to the disease progression or death from any cause. Patients who have not progressed or died are censored at the date last known progression-free. Patients with no on-study assessment will be censored at the time of registration.

Overall survival (OS): OS is defined as the time from randomization to death. Alive patients are censored at the date last known alive.

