10.2 Analysis datasets

Safety Population: The safety analysis dataset will include all eligible patients who begin treatment and receive at least one dose of protocol therapy. Patients will be analyzed in the cohort to which they were enrolled.

Efficacy Evaluable Population: All evaluable patients will be included in the analysis of efficacy endpoint. The term evaluable is defined as any eligible patient who receives at least one dose of protocol therapy and does not withdraw consent until the patient's first response assessment. Patients who fail to have a response assessment due to early progression or death will be categorized as non-responders.

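### Peak HAI is tested against PFS as if known at time zero, but the last titre that can set it is drawn about 20 weeks (control) or 4 weeks (experimental) after the PFS clock starts

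*Combined protocol and SAP*

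**What the plan says.** Section 10.4.5 closes with Kaplan-Meier and log-rank methods and the statement that a "Cox model will be used to test the relationship between peak HAI and PFS". It does not define peak, and gives no grouping, landmark or time-dependent term.

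The other relevant statements are these:

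- **Titres.** Section 1: "HAI will be measured in all patients at baseline, week 5, and week 21".
- **PFS.** Section 9: "Defined as the time from last treatment to the disease progression or death from any cause". It does not say whether treatment means the vaccine or myeloma therapy.
- **Last dose, control arm.** Section 6.1.2: "Fluzone HD vaccine once at the time of enrollment for a total of 1 dose".
- **Last dose, experimental arm.** The schema and section 6.5 place doses at weeks 1, 9 and 17. A footnote to 6.5 agrees, putting extra draws one week after each dose: "week 2 for control arm and weeks 2, 10, and 18 in the experimental arm". Those draws were for a subset, and the plan does not say that HAI is run on them.
- **Follow-up.** Section 5.3: "patient records will be reviewed until death or 2 years from enrollment (whichever comes first) to assess progression and survival".
- **Missing assessments.** Section 10.2: "Patients who fail to have a response assessment due to early progression or death will be categorized as non-responders".

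**The concern.** A covariate in a Kaplan-Meier, log-rank or ordinary Cox analysis should be known when the clock starts. Peak HAI is not. It is a maximum over draws, and the last of them falls after patients are already at risk of a PFS event.

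A maximum over three titres can never be lower than the maximum over the first two. A patient who dies before week 21, or misses that draw because of progression, therefore has a peak taken from fewer chances. In the experimental arm the missing draw is also the only scheduled HAI measurement after doses 2 and 3. Early events drift toward lower peaks, and high HAI can look protective when it has no effect. This is immortal-time bias.

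At stake is a possible report that a stronger vaccine response marks better disease control, when the sampling schedule contributed to the association.

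**Working it through.** **The plan's own figures.** The documents give no sample size, event count or power for this analysis. The trial size comes from section 10.3, and its 134 reproduces. The logistic-regression formula for a binary covariate (0.333 against 0.585, equal arms, two-sided 0.05, 80% power) gives 120.4, and 120.4/(1 − 0.1) = 133.8. I used the planned total of 148.

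**Gap between clock and last draw** (last treatment read as last vaccine dose). Control: 21 − 1 = 20 weeks. Experimental, fully dosed: 21 − 17 = 4 weeks. If dosing stops early the gap is longer. It is longer still if last treatment means earlier myeloma therapy.

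**Share with an event before the week-21 draw.** The documents give no PFS rate, so median PFS of m months is an assumption. With exponential PFS the share is 1 − 2^(−20/(m × 52.18/12)):

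- m = 12: 1 − 2^(−0.383) = 23%
- m = 24: 1 − 2^(−0.192) = 12%
- m = 48: 1 − 2^(−0.096) = 6%
- m = 60: 1 − 2^(−0.077) = 5%

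**Simulation with no true link.** 4,000 trials per scenario, 148 patients 1:1, PFS independent of titre, clock at the last dose received, follow-up to 104 weeks. Peak is the maximum of the titres actually drawn, split at its median.

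Assumed log2 titres:

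- Baseline: mean 4.3, SD 1.5.
- Week 5: baseline plus a non-negative rise, from a normal with mean 1.2 and SD 1.3 cut at zero.
- Week 21: mean change from week 5 of +0.5 (SD 1.0) in the experimental arm and −0.7 (SD 0.8) in controls.

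A quarter of PFS events are assumed to be deaths. Where draws stop only at death, patients who progress before their last dose have no valid PFS time on this clock and are dropped.

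| Median PFS (months) | Draws stop at progression or death: HR, rejection (protective side) | Draws stop only at death: HR, rejection | Week-21 landmark: HR, rejection |
|---|---|---|---|
| 12 | 0.88, 11.0% (10.6%) | 0.97, 5.9% | 0.99, 5.9% |
| 24 | 0.90, 7.4% (6.6%) | 0.97, 5.3% | 1.00, 5.2% |
| 48 | 0.91, 6.1% (4.9%) | 0.97, 5.1% | 1.00, 4.8% |

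The nominal protective-side rate is 2.5%. The simulation standard error at 5% is √(0.05 × 0.95/4000) = 0.34 percentage points. The landmark column is for draws that stop at progression or death.

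By arm, when progression stops the draws, the spurious hazard ratio is 0.81 to 0.85 in the experimental arm and 0.91 to 0.93 in controls.

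**Sensitivity.** A further set of runs on the same clock gave about 7% to 18% rejection and hazard ratios of 0.82 to 0.86 for medians of 48 to 12 months if progression stops draws. It gave about 5% and 0.98 to 0.99 if only death does. A titre pattern with SD 1.5, correlation 0.6, and means 4 at baseline, 5 at week 5 and 5.8/4.6 (experimental/control) at week 21 reproduces the upper end. In the death-only case the hazard ratio moves by a few hundredths with the handling of patients who progress before their last dose.

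**If patients with no week-21 titre are left out but the section 9 clock is kept**, the hazard ratio becomes about 1.03 to 1.06. Everyone retained is event-free to week 21. For controls that guarantees 20 weeks on the clock, for experimental patients only 4, and experimental patients hold more of the high peaks.

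**With the landmark**, the hazard ratio is about 1.00 and rejection about 5% in every scenario.

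**The case against.** The strongest reply is that progressors still give the week-21 sample. Section 6.5 schedules that blood for everyone, section 1 says HAI is measured in all patients, and section 5.2 does not name progression as a reason to leave the study. Only a general clause on changes in the patient's condition could cover some progressors. If only deaths lose the draw, the inflation is negligible. Early deaths should also be few: section 4.2 excludes "Expected survival < 9 months", and section 4.1 admits any plasma cell dyscrasia that meets the diagnostic criteria, which may include low-risk precursor conditions. All of this stands, and it is why the size must be stated conditionally.

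Three stronger readings are tempting, and the documents do not support them:

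- A reader might infer that being event-free to week 21 is required for a high peak. It is not. The peak can fall at week 5, particularly after a single dose. The bias is a shift in probability.
- A reader might infer that section 10.2 puts early progressors in a low-peak group. Its sentence sets a binary non-responder label for the efficacy endpoint. It assigns no titre and does not say that progressors skip week 21. Section 10.3 treated patients who missed week 21 as not evaluable, but those misses were due to COVID-19, so they do not settle the matter either.
- A reader might infer that a false link is demonstrated. Event rates, titres and the pattern of missing draws are all assumed here, and the median split is mine because the plan gives no cut-point.

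What the reply does not remove is the structure. The covariate is completed after the clock starts, and the plan has no rule for a missing week-21 titre. The proportional-hazards check in section 10.4.6 does not correct this.

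**Conclusion.** The point holds as a structural flaw of uncertain and probably modest size. As written, the analysis can favour higher HAI with longer PFS when there is no link. Over assumed medians of about 12 to 60 months, null rejection is roughly 6% to 18% (hazard ratio about 0.82 to 0.91) if progression stops draws, and close to 5% (about 0.97 to 0.99) if only death does. Dropping patients without a week-21 titre is not a clean remedy, because the section 9 clock then produces a small bias the other way.

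These figures rest on reading last treatment as the last vaccine dose, on exponential PFS and on assumed titres. The analysis is unpowered and not primary. The week-21 seroprotection comparison and the sample size are untouched. This is a cheap improvement, not a threat to the trial's main conclusion.

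**What to change.** In section 10.4.5, define peak HAI as the highest of the baseline, week-5 and week-21 titres. Replace the PFS sentence with a landmark analysis: among patients alive and progression-free with a titre at week 21, relate peak HAI to PFS counted from the week-21 visit, stratified by arm. Optionally add a Cox model with HAI as a time-dependent covariate.

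The cost is a sentence or two in the plan, with no new data or visits. Events before week 21 leave this analysis: about 5% to 23% of patients for assumed median PFS of 60 to 12 months. Patients who missed the week-21 draw for other reasons also leave, including the 27 of 50 in the first season, whom section 10.3 already counts as not evaluable. The section 9 definition can stay as it is for the other PFS analyses.
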